5.3.1.1 Study Procedures

The study procedures outlined in Appendix C are discussed in detail in this section, with the exception of study drug dispensing/compliance/accountability (Section 5.5.7), contraception counseling/contraceptive dispensing (Section 5.2.4), the collection of concomitant medication (Section 5.2.3) and adverse event information (Section 6.0). All study data will be recorded on the eCRF with the exception of the e-Diary, select PRO data and data from central lab/imaging vendor.

The Screening Period will occur within approximately 1.5 to 4 months prior to administration of the first dose of study drug on Day 1 (randomization). For procedures repeated during the Screening Period (as allowed per protocol or at the discretion of the AbbVie TA MD), the procedure performed closest to dosing will serve as a baseline for clinical assessment.

Study procedures during the Treatment and Follow-Up Periods may be performed within the visit windows specified in the applicable sections of the protocol. Scheduled monthly visits during the Treatment and Follow-Up Periods are based on a 28-day month. All scheduled study visits during the Treatment and Follow-Up Periods should occur within \pm 5 days of the projected date. However, the TVU, DXA scan, PAP test and endometrial biopsy may be performed within approximately \pm 15 days around the scheduled Treatment Month visit.

This protocol provides recommendations regarding the sequence of procedures to be performed during the study. In no case should these recommendations outweigh clinical

judgment or standard of care. If the protocol indicates that the AbbVie TA MD is to be contacted prior to performing a procedure, yet the timing of the request would either interrupt a procedure or would interfere with standard of care and clinical judgment, then clinical judgment should prevail and the AbbVie TA MD should be notified afterwards.

[figure not shown]
Informed Consent

The IRB/IEC approved informed consent will be signed by the subject before discontinuing any hormonal contraception/therapies or other prohibited medications or performing any study-specific procedures. Pharmacogenetic (PG) testing is optional and a subject must be provided a separate informed consent form for this blood and endometrial biopsy sample collection. Details about how informed consent will be obtained and documented are provided in Section 9.3.

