An electronic patient-recorded outcomes device (e-Diary) will be provided to all subjects during Screening, and subjects will record daily entries through Treatment Month 12. The e-Diary contains training information for the subject and/or site staff will provide training on the required entries in the e-Diary. Subjects will also be instructed to complete the diary at approximately the same time(s) every day throughout the Screening Period through Month 12 of the Treatment Period, including prior to study visits as applicable. The e-Diary will also remind subjects about consistent use of acceptable forms of non-hormonal contraception.

Site staff should review subject e-Diary data periodically beginning at Screening through Treatment Month 12, as well as at every study visit, to ensure subject comprehension and completion. Subjects who are screen failures will be instructed to return the e-Diary device to the site. All subjects will be instructed to return the e-Diary device to the site at the Treatment Month 12 study visit or at the Premature Discontinuation visit (if prior to Treatment Month 12).

Subjects will use the e-Diary to record assessments of DYS, NMPP, dyspareunia and uterine bleeding, as well as the use of protocol-allowed rescue analgesic medications for

endometriosis-associated pain. Scores from these daily assessments collected during Screening will be used to evaluate subject eligibility for the study prior to randomization on Day 1. These assessments will continue to be completed daily through Month 12 of the Treatment Period or until a subject prematurely discontinues from the Treatment Period (if they discontinue prior to Treatment Month 12).

Based on the subject's response to the question "Did you have your period in the last 24 hours?" in the daily e-Diary, the subject will be asked to assess either their dysmenorrhea or non-menstrual pelvic pain as follows:

Dysmenorrhea (DYS)

[figure not shown]
Subjects will be asked to assess their DYS and its impact on their daily activities. Subjects will be prompted to "Choose the item that best describes your pain during the last 24 hours when you had your period."

None	No discomfort.
Mild	Mild discomfort but I was easily able to do the things I usually do.
Moderate	Moderate discomfort or pain. I had some difficulty doing the things I usually do.
Severe	Severe pain. I had great difficulty doing the things I usually do.

Non-Menstrual Pelvic Pain (NMPP)

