The C-SSRS is a systematically administered instrument developed to track suicidal adverse events across a treatment study. The instrument is designed to assess suicidal behavior and ideation, track and assess all suicidal events, as well as the lethality of attempts. Additional features assessed include frequency, duration, controllability, reason for ideation, and deterrents. The Screening-Baseline C-SSRS questionnaire will be administered by site staff at Screening and on Day 1 (prior to randomization). The C-SSRS, Since Last Visit questionnaire should be administered by site staff during the Treatment Period as indicated in Appendix C.

During Screening or at the Day 1 visit, prior to randomization, any subject noted to have suicidal ideation within the last year, either via answering "yes" to question 4 and/or question 5 to the suicidal ideation portion of the C-SSRS, or via clinical interview, is not eligible for randomization. Following randomization, if the subject expresses suicidal ideation on the C-SSRS or via clinical interview at any time during the study, the Investigator should immediately notify the AbbVie TA MD. Appropriate steps will be taken to protect the subject (including possible discontinuation from the study and referral for appropriate psychiatric care). The C-SSRS administered at the Day 1 visit will serve as the baseline for clinical assessment.

Opioid Risk Tool (ORT)¹⁵

The Opioid Risk Tool (ORT) is a self-report screening tool designed to assess risk for opioid abuse among individuals prescribed opioids for treatment of chronic pain. The ORT will be administered to subjects and scored by site staff at the Screening visit. Subjects with a score of 8 or higher are not eligible for randomization.

Health Care Resource Utilization (HCRU)

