5.4.1 Discontinuation of Individual Subjects

In the event that a subject withdraws or is prematurely discontinued from study drug treatment, the subject should complete the Premature Discontinuation Visit as soon as possible (preferably within 2 – 7 days after last dose of study drug, if possible) and undergo study procedures as outlined in Appendix C. These procedures should not interfere with the initiation of any new treatments or therapeutic modalities the Investigator determines are necessary to treat the subject's condition. The reason(s) for the discontinuation from the Treatment Period will be recorded. Subjects who prematurely discontinue at the time of or after the Month 6 visit during the Treatment Period are expected to enter the Follow-Up Period for 12 months unless discontinuing due to pregnancy.

If a subject becomes pregnant during the Treatment Period or within 30 days of the last dose of study drug, no additional study procedures, except an ultrasound will be conducted. Refer to Section 6.1.4 for instructions on reporting of a pregnancy to the Sponsor and the required follow-up on the subject and fetus/infant.

If a subject requires surgery (e.g., laparoscopy, hysterectomy, ovarian cystectomy) for the management of their endometriosis during the Treatment Period, study drug should be discontinued and the Premature Discontinuation visit should be completed prior to surgery, if possible.

If a subject is discontinued from the study with an ongoing adverse event or an unresolved laboratory result that is clinically significant (as determined by the Investigator), the Investigator will attempt to provide follow-up until a satisfactory clinical resolution of the laboratory result or adverse event is achieved.

If a subject is being discontinued from the study prior to the completion of Treatment Month 6 time point, a mammogram (only for subjects \geq 40 years of age), DXA, TVU, Pap test, or endometrial biopsy does not need to be performed.

In addition, if a subject is being discontinued from the study due to a documented Z-score or T-score result of < -2.5, BMD decrease from baseline of > 8%, or TA MD assessment, an additional DXA scan does not need to be performed as a part of the Premature Discontinuation visit procedures.

Upon discontinuation from the Treatment Period, all used and unused study drug containers should be returned to the study site.

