Dispense Study Drug			X			X			

			Treatmen	t Period		
Activity	Month 37	Month 38	Month 39	Month 40	Month 41	Month 42
Phone Contact	X	X		X	X	
Vital Signs			X			X
DXA ¹						X
Pregnancy Tests: j,k,l urine (u) serum (s)	X (u)					
Lipids and Subset of Chemistry Labs: ALT, AST & Alkaline Phosphatase			X			X
Urine Test for Gonorrhea and Chlamydia (Optional) ⁿ						X
Pharmacokinetic Sample (elagolix and norethindrone concentration)						X
Pharmacodynamic Sample (E2)						X
Health Care Resource Utilization (HCRU)						X
 Endometriosis Health Profile-30 (EHP-30) PROMIS Fatigue Short Form 6a Work Productivity and Activity Impairment Questionnaire: Specific Health Problem (WPAI:SHP) 						X
Columbia-Suicide Severity Rating Scale (C-SSRS) – Since Last Visit			X			X
Smoking/Alcohol Assessment						X
Overall endometriosis-associated pain via NRS ^p	X	X	X	X	X	X
Review Adverse Events & Analgesic Rescue/Concomitant Medication	X	X	X	X	X	X
Contraceptive Counseling/Contraceptive Dispensing (prn)	X	X	X	X	X	X
Birth Control Attestation			X			X
Dispense Study Drug			X			X

	Treatment Period ^a						
Activity	Month 43	Month 44	Month 45	Month 46	Month 47	Month 48	PD^q
Phone Contact	X	X		X	X		
Physical Exam						X ^h	X ^h
Gynecological (External Genitalia, Pelvic and Breast) Exam						X ^h	X ^g
Vital Signs			X			X	X^h
Pap smear						X	X ^q
TVU ^j						X	X ^q
Mammogram ⁱ						X	X^q
DXA						X	X ^q
Pregnancy Tests: j,k,l urine (u) serum (s)	X (u)	X (u)	X (u)	X (u)	X (u)	X (u)	X (u)
Endometrial Biopsy ^m						X	X ^q
Lipids and Subset of Chemistry Labs: ALT, AST & Alkaline Phosphatase			X				
Clinical/Safety Labs: Chemistry, Hematology, Lipid Panel & Urinalysis						X	X
Urine Test for Gonorrhea and Chlamydia (Optional) ⁿ						X	X
Pharmacokinetic Sample (elagolix and norethindrone concentration)						X	X
Pharmacodynamic Sample (E2)						X	X
Pharmacogenetic endometrial sample (optional)							X
 Endometriosis Health Profile-30 (EHP-30) PROMIS Fatigue Short Form 6a 						X	X
Work Productivity and Activity Impairment Questionnaire: Specific Health Problem (WPAI:SHP)							

	Treatment Period ^a						
Activity	Month 43	Month 44	Month 45	Month 46	Month 47	Month 48	PD^q
Smoking/Alcohol Assessment						X	
Columbia-Suicide Severity Rating Scale (C-SSRS) – Since Last Visit			X			X	
Health Care Resource Utilization (HCRU)						X	X
Overall endometriosis-associated pain via NRS ^p	X	X	X	X	X	X	X
Review Adverse Events & Analgesic Rescue/Concomitant Medication	X	X	X	X	X	X	X

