3.4 Safety Endpoint(s)

The safety endpoints will be based on the following evaluations:

- Adverse events Monitoring
- Clinical laboratory tests
- Dual energy X-ray absorptiometry (DXA) scan
- Vital signs
- Endometrial biopsy
- Pelvic ultrasound (transabdominal ultrasound [TAU]/transvaginal ultrasound [TVU])
- Columbia Suicide Severity Rating Scale (C-SSRS)
- Pregnancy
- Uterine bleeding measured by e-Diary

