9.5 Other Safety Analyses

9.5.1 Columbia Suicide Severity Rating Scale (C-SSRS)

The C-SSRS data will be summarized as observed by treatment group.

The C-SSRS – Baseline/Screening measured at Day 1 will be considered as Baseline C-SSRS. Baseline C-SSRS will be summarized. Other analysis of C-SSRS will only include subjects who have at least 1 post-baseline C-SSRS measurement, regardless of whether they had a baseline C-SSRS measurement. The number of subjects with suicidal ideation, suicidal behavior, and self-injurious behavior without suicidal intent at each scheduled assessment during the appropriate Treatment Period will be summarized. In addition, this table will be repeated for providing a summary of lifetime outcomes and past year outcomes at screening and Day 1. No statistical test will be performed.

The number of subjects with suicide-related treatment-emergent events based on the C-SSRS during the appropriate Treatment Period will be summarized. No statistical tests will be performed.

A listing of subjects with suicidal ideation, suicidal behavior, or self-injurious behavior without suicidal intent based on the C-SSRS during treatment period will be provided.

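### Appendix C marks no C-SSRS at the Premature Discontinuation visit, so the last scheduled structured suicidality check can fall up to 84 days before stopping (minor, cheap to fix)

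*Protocol*

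**What the plan says.** Protocol Appendix C sets the baseline form of the C-SSRS at Screening and Day 1. The on-treatment form, listed as "Columbia-Suicide Severity Rating Scale (C-SSRS) – Since Last Visit", is set at Months 3, 6, 8, 10 and 12, then at every on-site visit from Month 15 to Month 48. In the block for Months 43-48 and PD, that row carries marks at Months 45 and 48 and none under PD.

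The body text adds no assessment. Protocol 5.3.1.1 says the "Since Last Visit questionnaire should be administered by site staff during the Treatment Period as indicated in Appendix C". Protocol 5.4.1 has women who stop early "undergo study procedures as outlined in Appendix C". The Follow-Up grid has no C-SSRS row. Under 5.4.1, only women who stop "at the time of or after the Month 6 visit during the Treatment Period are expected to enter the Follow-Up Period", so for earlier stops PD is the last scheduled visit.

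On the analysis side, SAP 3.4 includes the C-SSRS in the list introduced by "The safety endpoints will be based on the following evaluations". SAP 9.5.1 describes the data by scheduled assessment without testing. Beyond the baseline summary, its analyses "will only include subjects who have at least 1 post-baseline C-SSRS measurement, regardless of whether they had a baseline C-SSRS measurement".

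**The concern.** The protocol uses the C-SSRS to follow suicidal events through the study (5.3.1.1). Ideation, whether found on the scale or at interview, is a ground for withdrawal (5.4). A woman whose ideation begins after her last scheduled C-SSRS, and who then stops, is not asked the graded questions at exit, although she is already at a study visit with trained staff.

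Two things are at stake: a structured safety check at the point of leaving, and the completeness of the C-SSRS data. A woman who stops before Month 3 has no scheduled post-baseline C-SSRS. SAP 9.5.1 therefore leaves her out of the post-baseline summaries unless an unscheduled one was done.

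**Working it through.** The documents state no C-SSRS interval, so there is no figure to reproduce. The gaps follow from the schedule.

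**Inputs**
- Month length: 28 days (Protocol 1.3 and 5.3.1.1).
- Visit window: "All scheduled study visits during the Treatment and Follow-Up Periods should occur within" 5 days either side of the projected date (5.3.1.1; also Appendix C footnote a). Day 1 is the anchor and has no window.
- Post-baseline C-SSRS visits (Appendix C): Months 3, 6, 8, 10, 12 (5 visits) and 15, 18, ..., 48 (12 visits), giving 5 + 12 = 17, none at PD.
- PD visit: preferably 2-7 days after the last dose (5.4.1).

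**Formula.** Nominal gap = (difference in months) x 28. The largest gap with windows adds 5 + 5 = 10 days (one visit early, the next late), or 5 days when the interval starts at Day 1.

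| Interval | Nominal (days) | With windows (days) |
|---|---|---|
| Day 1 to Month 3 | 3 x 28 = 84 | 84 + 5 = 89 |
| Month 3 to 6 | 84 | 84 + 10 = 94 |
| Months 6-8, 8-10, 10-12 | 2 x 28 = 56 | 56 + 10 = 66 |
| Month 12 to 15, and each later interval to Month 48 | 84 | 94 |

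These are the longest times from the last scheduled C-SSRS to stopping, for a woman who attends as scheduled. A missed or pandemic-delayed visit would lengthen them. Counted to the PD visit, the nominal figures become 86-91 and 58-63 days. By comparison, adverse event review is at most 28 days apart (28 + 10 = 38 with windows) and is repeated at PD.

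**Is the PD cell really empty?** The C-SSRS row has seven cells for seven columns, and the last is blank. The next three rows (health care resource use, overall pain score, adverse event review) are marked under PD. This makes a lost column unlikely but does not rule out a lost mark.

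**Comparison with the other safety evaluations.** SAP 3.4 lists nine:
- Adverse events, laboratory tests, vital signs and pregnancy are marked at PD (4).
- DXA, ultrasound and endometrial biopsy are marked at PD subject to footnote q (3).
- Uterine bleeding is in the e-Diary, "completed daily through Month 12 of the Treatment Period or until a subject prematurely discontinues from the Treatment Period" (1).
- The C-SSRS has neither (1). Total: 4 + 3 + 1 + 1 = 9.

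**Reach of a change now.** Protocol 5.3.1.1 (Endometrial Biopsy) states that all subjects are past Month 36. At most four intervals remain: 4 x 84 = 336 days. If stops were spread evenly within an interval (an assumption), the mean time since the last C-SSRS would be 84/2 = 42 days. Stops triggered by a DXA or biopsy result would tend to have shorter gaps, because those procedures fall at visits that carry a C-SSRS.

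**The case against.** The case against rests on five points.

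- **One cell, uncertain text.** The pregnancy-test row for Months 37-42 shows a single mark, although footnote l requires home tests at Months 37-38 and 40-41. The PD column is also not a full inventory: 5.3.1.2 calls for DNA/RNA blood at PD, and the grid has no row for it. This stands, and is why the original table must be checked first.
- **The blank may be deliberate.** Smoking/alcohol assessment and birth control attestation are also blank at PD. Footnote q accepts DXA, ultrasound and biopsy results up to six months old at exit, older than an 84-day C-SSRS. This stands. A reader might infer a drafting error, but the documents do not show one.
- **Other cover exists.** Adverse events are reviewed at PD and collected to 30 days after stopping (6.1.4). Neuro-psychiatric events are of special interest (6.1.1.3), and SAP Appendix B includes a depression and suicide/self-injury query. Ideation expressed at interview at any time goes to the sponsor's medical director (5.3.1.1). Recent severe ideation and past attempts are excluded at entry (5.2.2). So the documents do not support the inference that suicidality goes unmonitored at exit. What is missing is the graded instrument.
- **Limited reach.** Only open-label stops between Month 36 and Month 48 can benefit, fewer once approval time is counted. This stands, and it holds the point to a minor one.
- **Cost beyond one cell.** An amendment needs ethics approval (9.1) across about 200 sites. This stands if the change is made alone, much less if it is combined with another.

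**Conclusion.** The gap is real as the extracted schedule reads. No C-SSRS is marked at PD and no other text supplies one, so the last scheduled structured check can precede stopping by up to 84 days (56 in Months 6-12; 94 and 66 with windows; 89 for Day 1 to Month 3). This rests on the PD cell being blank in the original table and on scheduled visits being attended.

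It is a minor point: other cover exists, few exits can still be reached, and the blank may be intended. Three stronger readings are not supported:

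- **Harm to inference.** SAP 9.5.1 specifies no tests, so no test, alpha or power is affected.
- **A stated number of women.** The documents give no dropout rate, so no count can be claimed.
- **A required count by arm of women with no post-baseline C-SSRS.** It could be useful, but it can be derived from the Safety Analysis Set and the number included under SAP 9.5.1. It is optional reporting.

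**What to change.** 1. Check the PD cell of the C-SSRS row in the original Appendix C. If it is blank, mark the since-last-visit form under PD, bundled with any other amendment. The last structured check would then fall at the PD visit itself, preferably 2-7 days after the last dose.
2. In SAP 9.5.1, show PD records as their own row in the by-visit C-SSRS summary. That summary is organised by scheduled assessment, and a PD record will usually fall between scheduled months. A PD record already counts as a post-baseline measurement, so the inclusion rule needs no change.

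Cost: a slightly longer exit visit, a schedule amendment with ethics approval, and one added table row. Site staff already administer the form, and the pandemic provisions in 5.3.1.1 allow it by phone or video.

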Appendix D. BI-RADS Classification

[figure not shown]
The BI-RADS assessment categories are:

- \bullet 0 Incomplete
- 1 Negative
- 2 Benign findings
- 3 Probably benign
- 4 Suspicious abnormality
- 5 Highly suspicious of malignancy
- 6 Known biopsy with proven malignancy

[figure not shown]

Appendix E. Overall Endometriosis-Associated Pain Questionnaire

Within the past 7 days on a scale of 0 - 10, 0 being no pain and 10 being worst pain ever, how do you rate your endometriosis pain?

[figure not shown]

Appendix F. Patient Global Impression of Change (PGIC) Since I started taking the study medication, my endometriosis related pain has: Very much improved Much improved Minimally improved Not changed Minimally worse Much Worse Very much worse

Appendix G. Dietary Calcium Intake Questionnaire

Food Type	Standard Serving Size	Number of Servings on Average
Dairy		
Skim Milk (non-fat)	8 ounces	
Soy milk (calcium-fortified)	8 ounces	
2% Milk	8 ounces	
Whole Milk	8 ounces	
Milk (buttermilk, lowfat)	8 ounces	
Yogurt (plain, low fat)	8 ounces	
Yogurt (fruit, low fat)	8 ounces	
Frozen yogurt (vanilla, soft serve)	1/2 cup	
Ice cream (vanilla)	½ cup	
Mozzarella cheese (part skim)	1 ½ ounces	
Cheddar cheese	1 ½ ounces	
Sour cream (reduced fat)	2 tablespoons	
Cottage cheese (1% milk fat)	1 cup	
Cream cheese (regular)	1 tablespoon	
Vegetables, Fruits, Nuts and Beans		
Turnip greens (fresh, boiled)	1/2 cup	
Broccoli (raw)	1/2 cup	
Kale (fresh, cooked)	1 cup	
Kale (raw, chopped)	1 cup	
Chinese cabbage (bok choy raw, shredded)	1 cup	
Orange juice (with calcium)	6 ounces	
Fish and Tofu		
Sardines (canned in oil, with bones)	3 ounces	
Canned pink salmon (with bones)	3 ounces	
Tofu (soft, made with calcium sulfate)	1/2 cup	
Tofu (firm, made with calcium sulfate)	1/2 cup	

Food Type	Standard Serving Size	Number of Servings on Average
Other		
Ready to eat cereal (calcium-fortified)	1 cup	
Bread (white)	1 slice	
Bread (whole-wheat)	1 slice	
Tortilla (corn, ready to bake/fry)	one 6" diameter	
Tortilla (flour, ready to bake/fry)	one 6" diameter	
Chocolate Pudding (refrigerated ready to eat)	4 ounces	

[figure not shown]
Note: National Institutes of Health 2016. 16

Appendix I. Analgesic Change During Treatment Period

Use of	No Analgesics at Baseline	
Analgesic used during Screening	Analgesic dose status at end of study	Responder?*
None	None	Responder
	Opioid analgesic and/or NSAID is started	Nonresponder
Use o	f Only NSAID at Baseline	
Analgesic used at Baseline	Analgesic dose status at end of study	Responder?*
NSAID	Dose stopped, decreases, or is stable**	Responder
	Dose increases by 15% or more	Nonresponder
	Opioid analgesic is substituted or added	Nonresponder
Use of Onl	y Opioid Analgesic at Baseline	
Analgesic used at Baseline	Analgesic dose status at end of study	Responder?*
Opioid analgesic	Dose stopped, decreases, or is stable**	Responder
	Dose stopped and NSAID substituted (any dose)	Responder
	Dose decreases and NSAID added (any dose)	Responder
	Dose stable** and NSAID added (any dose)	Nonresponder
	Dose increases by 15% or more	Nonresponder
Use of NSAID	and Opioid Analgesic at Baseline	
Analgesics used at Baseline	Analgesic dose status at end of study	Responder?*
NSAID + opioid analgesic	NSAID dose stops + opioid analgesic use stops, decreases, or is stable**	Responder
	NSAID use stops + opioid analgesic dose increases by more than 15%	Nonresponder
	NSAID dose decreases + opioid analgesic use stops, decreases, or is stable**	Responder
	NSAID dose decreases + opioid analgesic dose increases by more than 15%	Nonresponder
	NSAID dose stable** + opioid analgesic use stops, decreases, or is stable**	Responder
	NSAID dose stable** + opioid analgesic dose increases by more than 15%	Nonresponder

Use of No Analgesics at Baseline				
Analgesic used during Screening	Analgesic dose status at end of study	Responder?*		
	NSAID dose increases by more than 15% + opioid analgesic use stops	Responder		
	NSAID dose increases by more than 15% + opioid analgesic dose decreases	Responder		
	NSAID dose increases by more than 15% + opioid analgesic dose is stable**	Nonresponder		
	NSAID dose increases by more than 15% + opioid analgesic dose increases by 15% or more	Nonresponder		

^{*} Analgesic Responder = Defined as a subject who meets the criteria for no increase in analgesic use.

^{**} Stable = Dose is the same as the baseline dose or increases by less than 15% of the baseline dose.
